### 8.2.2 Cost-Effectiveness Analyses (Aim 2)

We will estimate and compare the unit cost (per patient) of the SNaP intervention under SA or TA. Second, if there is a difference in effectiveness between arms (and the more effective option is also the more expensive one), we will conduct a comparative cost-utility analysis to identify the economically preferred option, assuming a willingness to pay of Vietnam's per-capita gross national income (GNI) per disability-adjusted life year (DALY) averted.

**Cost analysis:** The primary outcome will be a unit cost per patient covered and per ART uptake under SA or TA, reported both as an average cost (relative to no SNaP intervention) and an incremental cost (of tailored implementation relative to standard implementation), using the empirical cost measurements, as described above. We will also describe the major cost components and key drivers of cost (e.g., patient volume or cost of ART), and conduct sensitivity and scenario analyses around these major cost items to describe the likely variation in per-patient costs across different settings. For patient-level factors, we will use multivariable regression techniques (likely after log-transformation of cost measurements, depending on the distribution of the data) to develop cost functions that describe the relationships between patient-level variables (e.g., gender, distance from clinic) and patient costs under each implementation strategy.

**Cost-utility analyses:** We will construct a Markov model to convert the incremental cost per ART uptake (primary cost-effectiveness outcome) into an estimated incremental cost per disability-adjusted life year (**DALY**) averted. We will calibrate this model to the demographics of the trial population and incorporate a Markov structure, simulating 10,000 adults living with HIV over time steps of 6 months. Markov states will include engagement in care, ART status, viral suppression status, and engagement with MAT, and will project effectiveness outcomes observed in the trial over the lifetime of a cohort of simulated patients. We will incorporate into the model the annual probability of first-order transmission (*i.e.*, transmissions of HIV occurring from individuals in each arm). We will adopt the societal perspective, with secondary analyses from the health system and patient perspectives. We will conduct one-way sensitivity analyses across all model parameters, multi-way sensitivity analyses for those parameters found to be most influential, and a probabilistic uncertainty analysis in which all parameters are varied simultaneously using Latin Hypercube Sampling. Additional sensitivity analyses will include different assumptions about the duration of effectiveness of SNaP and scenario analyses of different economic and epidemiological conditions (*e.g.*, different country contexts). All analyses will be performed in R (R Foundation for Statistical Computing).

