## 2. STUDY OBJECTIVES AND DESIGN

### 2.1. Study Objectives

***The primary objectives of this study are:***

- 1) To compare the standard approach (SA) to tailored approach (TA) to scaling-up an integrated intervention, SNaP, for PWID in HIV test sites in Vietnam. (Aim 1)

We will conduct a two-arm, pragmatic cluster randomized implementation trial among HIV test sites in Vietnam. HIV test sites (n=42) will be randomized to receive one of two implementation approaches: a) SA—a standard, one size fits all multifaceted implementation package identified through Intervention Mapping, or b) TA—a tailored implementation package using Intervention Mapping with tailoring to each test site.

- The primary outcomes are HIV test site-level EBI fidelity (implementation outcome) and ART uptake (effectiveness outcome).
- Secondary implementation outcomes include penetration, acceptability, and cost.
- Secondary effectiveness outcomes include viral suppression and MAT use.
- We will conduct outcome assessments at 12 and 24 months.

- 2) To measure the incremental costs of SA compared to TA for SNaP implementation in Vietnam. (Aim 2)

Comprehensive costing of SA and TA will be performed using a micro-costing or “bottom-up” approach. This costing will include the intervention and the full implementation process, inclusive of Intervention Mapping and tailoring.

- The primary cost-effectiveness outcome will be the incremental cost-effectiveness ratio, expressed as the incremental cost per incremental ART uptake, comparing TA to SA.

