#### 8.1.2 *Effectiveness Outcomes Sample Size Calculations*

The **primary effectiveness outcome is ART uptake**, measured as a dichotomous variable at the PWID level. After accounting for up to 12% mortality during follow-up, we estimate an available sample of 6200 PWID, with cluster (test site) size ranging from 7-764 PWID (mean≈148). **Loss to follow-up does not affect this outcome**, as patients not retained in clinic will be assumed not to be on ART.

**To calculate the design effect**, we estimate that the intra-cluster correlation coefficient may range from 0.01-0.05, as is typical in clinic-level behavioral interventions, implying a design effect between 2.5 and 8.4.

Using two-tailed tests and  $\alpha=0.05$ , we will have >80% power to detect a difference as small as 10 percentage points (e.g., 70% vs. 60% ART uptake) if the ICC is as large as 0.05, and as small as 6 percentage points (e.g., 70% vs. 64% ART uptake) if the ICC is as small as 0.01. Thus, we are well powered to detect operationally meaningful differences in our primary effectiveness outcome of ART uptake.

For **viral load**, which is based on a sample of  $n=1200$  (~30 per clinic), assuming the same ICC of 0.01-0.05, we will have 80% power to detect differences of 10-14 percentage points in viral suppression between arms (e.g. 40% vs. 30% if  $ICC=0.01$ ; 40% vs. 26% if  $ICC=0.05$ ).

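### The cost-utility analysis runs only if effectiveness differs, in an undefined sense, and the better arm costs more; it should run whatever the results

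*Combined protocol and SAP*

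**What the plan says.** Section 8.2.2 first compares unit costs between the arms. Its second step carries a condition: "if there is a difference in effectiveness between arms (and the more effective option is also the more expensive one", then "we will conduct a comparative cost-utility analysis to identify the economically preferred option", at a threshold of one per-capita GNI for each DALY averted.

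The cost-utility paragraph of the same section opens "We will construct a Markov model to convert the incremental cost per ART uptake (primary cost-effectiveness outcome" into a cost per DALY averted. The model "will project effectiveness outcomes observed in the trial over the lifetime of a cohort of simulated patients". It also includes "a probabilistic uncertainty analysis in which all parameters are varied simultaneously using Latin Hypercube Sampling". That paragraph neither repeats nor removes the condition.

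Two results carry no condition:
- Section 2.1: "The primary cost-effectiveness outcome will be the incremental cost-effectiveness ratio, expressed as the incremental cost per incremental ART uptake, comparing TA to SA".
- Section 8.2.2, cost analysis: unit cost per patient covered and per ART uptake, as an average and as an increment.

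**The concern.** The condition depends on trial results, and the plan does not define it. *Difference* could mean a significance test, an interval or a point estimate. It could refer to ART uptake, or to viral suppression, MAT or engagement in care, all of which are states in the model. The choice could then be made after the results are known.

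The conditional step is the one that says whether tailoring is worth its cost. The rationale in Section 1.2 promises guidance to ministries whatever the trial shows, with cost among its components. If the condition fails, the plan does not say how the preferred approach is to be chosen.

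The cost half of the condition is also open. Section 4.2 (Description of Intervention Mapping) allows the tailored strategies at a clinic to be either lighter or heavier than the standard package. The better arm may therefore appear cheaper, by chance or in truth, and the uncertainty about that dominance would not be assessed.

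**Working it through.** **Inputs (Section 8.1.2 unless noted).** 6200 PWID, so 3100 per arm under 1:1 allocation of 42 sites (Section 2.2); mean site size 148; ICC 0.01 to 0.05; two-sided α of 0.05; 70% uptake in the better arm. The true gains of 3 and 5 points are assumptions for illustration.

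**The plan's own figures.**
- Design effect = 1 + (148 − 1) × ICC: 2.47 at ICC 0.01 and 8.35 at ICC 0.05. The plan gives 2.5 and 8.4.
- Effective n per arm = 3100 / design effect: 1255 and 371.
- Two-proportion power: 89.2% for 70% vs 64% at ICC 0.01, and 81.6% for 70% vs 60% at ICC 0.05. Both agree with the stated >80%.

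**Reading 1: a difference means p<0.05 on ART uptake.** Treat the estimated gain as Normal(d, SE), with SE = √[(p₁(1−p₁) + p₂(1−p₂)) / n_eff]. For d = 5 points at ICC 0.05:
- SE = √[(0.70×0.30 + 0.65×0.35)/371] = 3.43 points
- smallest significant gain = 1.96 × 3.43 = 6.73 points
- P(significant) = 1 − Φ(1.96 − 5/3.43) = 0.31, so the analysis is skipped in 69%
- mean gain given significance = d + SE × φ(a)/(1 − Φ(a)), with a = 1.96 − d/SE. This is 8.93 points, or 1.79 times the truth.

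**Reading 2: a difference means the point estimate.** P(wrong sign) = Φ(−d/SE).

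| ICC | True gain (points) | SE (points) | Skipped if p<0.05 needed | Mean gain if significant ÷ truth | Wrong sign |
|---|---|---|---|---|---|
| 0.01 | 3 | 1.85 | 63% | 1.63 | 5% |
| 0.01 | 5 | 1.87 | 24% | 1.15 | 0.4% |
| 0.01 | 6 | 1.87 | 11% | 1.06 | 0.1% |
| 0.05 | 3 | 3.41 | 86% | 2.81 | 19% |
| 0.05 | 5 | 3.43 | 69% | 1.79 | 7% |
| 0.05 | 6 | 3.44 | 59% | 1.54 | 4% |
| 0.05 | 10 | 3.48 | 18% | 1.11 | 0.2% |

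**What is left out.** These figures cover only the effectiveness half. The documents give no cost standard deviations, so the cost half cannot be quantified; it can only add to skipping.

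The figures also assume equal site sizes, whereas the plan expects 7 to 764 and gives no coefficient of variation. With an assumed value of 1.0, the design effect 1 + (2×148 − 1) × ICC becomes 3.95 and 15.75. Skipping at a true 5 points then rises to 44% and 82%.

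**The case against.** The strongest reply is that little is lost. Aim 2 is to measure incremental costs, and its primary cost-effectiveness outcome, the ICER per ART uptake, carries no condition. Computing no trade-off ratio when one arm is both cheaper and better is a defensible convention. The text names no p-value, and the paragraph on the Markov model does not repeat the condition. At the plan's design differences the selection is modest.

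Much of this stands, and it rules out three stronger inferences that a reader might draw.

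- **That Aim 2 as a whole is conditional.** It is not. Only the DALY conversion and the threshold decision are.
- **That joint uncertainty is ignored throughout.** The plan varies all parameters together whenever the cost-utility analysis runs. The gap arises when it does not run: the cost analysis then offers sensitivity and scenario analyses on cost items, not cost and effect together.
- **That the rule inflates the result.** One might invert 1.79 and say that cost per uptake is understated by 44% (1 − 1/1.79). But cost per uptake is reported whatever the outcome, and where the model runs, the same observed effect enters it with or without the condition. The factor describes the average of cost-utility results produced only after significance. It is not a bias added to this trial's estimate.

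The rest of the reply does not remove the point. The convention on dominance presumes that dominance is known, and here it would be estimated. If the Markov paragraph is meant to be unconditional, two parts of Section 8.2.2 disagree and must be reconciled.

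**Conclusion.** The condition is in the plan, is undefined and is not lifted elsewhere. Its effect is limited to the cost-utility step, which is nevertheless the step meant to identify the preferred approach.

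The size depends on a reading that the plan does not settle. Under a significance reading on ART uptake, the chance of skipping is about 24% to 69% for a true 5-point gain and 63% to 86% for a true 3-point gain, across the plan's ICC range. Cost-utility results produced only after significance would on average rest on a gain 1.15 to 1.8 times a true 5 points. Under a point-estimate reading, the wrong sign appears in 5% to 19% of trials at a true 3 points and rarely at the design differences.

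These figures rest on a normal approximation, 70% uptake in the better arm, equal site sizes and assumed true gains. The change is worth making because the model and its uncertainty analysis are already planned.

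**What to change.** In Section 8.2.2, delete the condition and state that the Markov model and the probabilistic analysis will be run whatever the effectiveness and cost results.

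Draw incremental cost and effect jointly, for example by resampling sites within arm, and pass those draws to the planned probabilistic analysis. Report incremental net benefit and the probability of cost-effectiveness at the stated GNI threshold alongside the ICER. If one arm appears dominant, report the probability of dominance instead of stopping there.

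The cost is a wording change and modest analyst time, including a model run even when the arms look similar. No data collection, randomisation or participant procedure changes.

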### **8.2.3 High and Low Performing and Sustaining Site Characterization- Analyses (Aim 3)**

**Aim 3 - Qualitative data analyses:** All qualitative interviews will be audiotaped, transcribed, translated, coded and computerized for analysis using Atlas.ti v.8 software. Analysis will begin as data are collected so that topics for further exploration can be incorporated into ongoing fieldwork. Qualitative data analysis consists of the search for patterns in data and conceptualizing ideas that help explain the presence of those patterns. Textual data analysis will involve five steps: 1) reading for content; 2) deductive and inductive coding; 3) data display to identify emerging themes; 4) data reduction; and 5) interpretation. Memos will be written for each code. Codes will be refined during the process of analysis. Responses of navigators and counselors, test site staff, and test site directors will be compared within and across the staff groups and within and across high and low performing and sustaining sites. For example, we will compare navigator and counselors' attitudes around implementing SNaP, including PWID-related stigma, competing job responsibilities at the site, perceived effectiveness of SNaP, and perceived status/value of being navigators and counselors, by high and low performing sites to understand if and how these attitudes may ultimately affect site performance.

**Aim 3 - Quantitative data analyses:** The site characteristics will be assessed with exploratory analyses to examine associations with high and low performing and sustaining clinics. Site is the unit of analysis. Given the small sample size, we will assess each site measure separately. We will use a generalized linear model with a logit link and binomial error distribution to assess the dichotomous outcome of high or low performance and sustainment. Individual implementation or demographic measures will be included as an explanatory variable, with an indicator variable for study arm, and an interaction term (assessed with  $\alpha=0.10$ ). The interaction term will aid in interpreting whether a specific characteristic modified the effect of the implementation strategy. Two sets of models will be constructed: baseline measures only and change from baseline to evaluation.

**Data triangulation:** IDI and quantitative data will be triangulated to understand SNaP

and SA and TA approaches within high and low performing and sustaining sites. For example, if in low performing sites, site directors scored low on the implementation leadership scale leading to low SNaP fidelity and penetration, the qualitative data could inform *why* site directors in these sites did not support and value SNaP (e.g. lack of prioritization of PWID clients due to PWID-related stigma), and *how* we can improve leadership investment (e.g. a stigma-reduction program combined with VAAC recognition of sites that improve SNaP implementation over a year). These integrated data will provide information about both clinics that “lag behind” and clinics that need less intervention for success. Although descriptive, these data will provide critical information for other settings seeking to implement and sustain SNaP.

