#### **5.1.4 Randomization**

We obtained a complete list of the 136 HIV test sites in Vietnam, including the number of persons tested per month, positivity rates, and proportion of PWID. These data have been used to identify 42 proposed test sites for inclusion in this implementation study.

Test sites will be stratified by region and size, then randomized to either arm at a 1:1 ratio (21 sites per trial arm). Randomization will be blocked within strata to ensure equal distribution by arm.

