Sustainment survey: We will administer the 3-question Provider REport of Sustainment Scale (PRESS) scale to site staff (including counselors and navigators) who were involved with the delivery of SNaP 6-10 months following the completion of the SNaP activities at each site. The purpose of the scale will be to assess the sustainment of the SNaP intervention at each of the sites, as well as characteristics of high and low sustaining sites. Study staff will contact site staff at the 42 HIV test sites that were involved in the SNaP study to invite them to participate in the survey. About 252 clinic staff (6 per site) will participate in the survey. Clinic staff who are interested in participating will be emailed electronic consents via a Qualtrics database to read and sign (if they choose to participate in the survey). They will then complete the fully self-administered survey on Qualtrics. The survey should take no more than 5 minutes to complete.

Sustainment in-depth interviews: We will conduct in-depth interviews with clinic navigators/counselors (n=12) and site staff or site directors (n=24) from a sub-sample of 12 of the SNaP scale-up sites at 6-month post-endline. Based on their scores on the PRESS, we will randomly select 6 “high sustainer” and 6 “low sustainer” clinics for these interviews. The purpose of these interviews is to understand how SNaP and SNaP implementation strategy adaptations influence normalization and sustainment of the SNaP intervention into HIV testing clinics after the removal of external study support. SNaP study staff will contact clinic navigators, site staff, and site directors and will invite them to participate in the interviews. All interviews will be conducted over Zoom in Vietnamese by bilingual Vietnamese research assistants trained in qualitative interviewing. Participants will provide informed consent before being interviewed. The interviews are expected to last approximately one hour. All interviews will be audio-recorded, transcribed verbatim, and translated to English.

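### Aim 3 models sustainment only as a high/low label with no pre-specified PRESS cut-off; modelling the graded site score would gain power at 42 sites unless scores are strongly skewed

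*Combined protocol and SAP*

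**What the plan says.** Section 5.4.1 describes the measure: "We will administer the 3-question Provider REport of Sustainment Scale (PRESS) scale to site staff". The survey goes to about 252 staff, six per site, and covers every site: "Study staff will contact site staff at the 42 HIV test sites that were involved in the SNaP study". Its aim is site-level: "The purpose of the scale will be to assess the sustainment of the SNaP intervention at each of the sites".

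The same section uses the scores to pick clinics for interview. It opens with "Based on their scores on the PRESS, we will randomly select 6" and goes on to six high-sustaining and six low-sustaining clinics. It does not say what score makes a clinic high or low, how staff answers become a site score, or what happens to sites in the middle.

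Section 8.2.3 gives the only quantitative Aim 3 model: a logit link with "binomial error distribution to assess the dichotomous outcome of high or low performance and sustainment". It adds "Site is the unit of analysis" and "Given the small sample size, we will assess each site measure separately". Each model holds one site measure, an arm indicator and their interaction, with the interaction assessed at alpha 0.10. The section calls these analyses exploratory.

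Performance, the companion label, has an a priori rule: a fidelity score of 136 and 70% ART uptake (Sections 5.4 and 7.5). Sustainment has no such rule.

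**The concern.** Two things are at issue, both confined to the sustainment outcome.

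- **The outcome is not defined.** Without a cut-off, the dependent variable of the planned regression cannot be built from the text. Two analysts could split the same 42 scores at different places and report different site characteristics.
- **Graded information is discarded.** Each site will have a mean over about six staff on a three-item scale. The interviews need high and low groups; a regression does not. With 42 units, and a plan that limits itself to one measure at a time because the sample is small, cutting the score generally works against finding which characteristics go with sustainment.

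At stake is how well the exploratory screen works, and how reproducible it is. The fidelity and ART uptake comparisons are not touched.

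**Working it through.** **Inputs from the documents.** 42 sites, 21 per arm (Section 5.1.4); site as the unit, one characteristic at a time, arm, interaction at alpha 0.10 (Section 8.2.3). The documents give no Aim 3 power, no alpha for a characteristic's main effect, no expected association, and no PRESS response format or distribution. Everything below about r (the correlation of a site characteristic with the site score), the split and the score's shape is therefore an assumption, shown over a range.

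**The plan's own site-level figure.** There is no Aim 3 figure to reproduce, so the 42-site basis was checked on fidelity (Section 8.1.1): difference 136 − 100.5 = 35.5, SD 40.
- Standardised difference = 35.5 / (40 × √(2/21)) = 2.88.
- Normal approximation: Φ(2.88 − 1.96) = 0.82. Exact noncentral t: 0.801.
- For 136 versus 111 with SD 28, the t test gives 0.806.

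The stated 80% reproduces.

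**Analytic check of the split.** A median split of a normal variable multiplies its correlation by √(2/π) = 0.798. Approximate power at two-sided 5% is Φ(atanh(r) × √39 − 1.96), with 39 = 42 − 3.
- r = 0.3: 49% on the score, 33% on the label; loss 16 points.
- r = 0.4: 75% and 54%; loss 21.
- r = 0.5: 93% and 75%; loss 18.

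**Simulation, main effect at 5%.** 42 sites, normal score y = r·x + √(1 − r²)·e, characteristic plus arm, 2,500 runs per cell. A linear t test on the score is compared with a logistic model on a median-split label.

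| r | Linear | Logistic, likelihood-ratio | Logistic, Wald | Loss (LR / Wald) |
|---|---|---|---|---|
| 0.2 | 24.5% | 19.6% | 15.6% | 5 / 9 |
| 0.3 | 49.2% | 36.6% | 30.8% | 13 / 18 |
| 0.4 | 74.9% | 57.9% | 51.8% | 17 / 23 |
| 0.5 | 92.4% | 77.3% | 73.0% | 15 / 19 |
| 0.6 | 99.1% | 92.2% | 89.3% | 7 / 10 |

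A further run gave 48/77/93% (linear) against 36/61/80% (likelihood-ratio) at r = 0.3/0.4/0.5, a loss of 12 to 16 points. Over r = 0.3 to 0.5, a 33/67 split loses 16 to 30 points and a 25/75 split 18 to 34 points (likelihood-ratio to Wald).

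**Shape of the score (median split, likelihood-ratio, r = 0.3/0.4/0.5).**
- Three bounded items from six staff per site: losses of 12 to 18 points in one set of runs and 9 to 17 in another. Item properties were assumed.
- 35% of sites tied at the maximum: about 8 to 9 points. One 1,200-run set gave 42/65/87% against 36/58/78%, so 6, 7 and 9 points. A 3,000-run check of the same setting gave 8 to 11.
- Strong left skew, −exp(−1.2y): 32/55/74% against 37/56/79%. No loss; the label does slightly better.

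**Planned interaction test at alpha 0.10 (median split, likelihood-ratio).**
- Normal score, slopes of −r and +r in the two arms, r = 0.3/0.4/0.5: 60.4/81.5/95.8% against 50.0/67.9/87.6%; losses 10, 14 and 8.
- Slopes 0 and 0.5, ceiling: 41% against 41%; loss nil.
- Slopes 0 and 0.5, strong skew: 37% against 43%; reversed.

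**Error rates under no association (normal score, median split).** Main effect at 5%: linear 4.9%, likelihood-ratio 6.4%, Wald 4.5%. Interaction at 10%: linear 9.3%, likelihood-ratio 12.7%, Wald 10.4%.

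**The case against.** **The binary model fits the question asked.** Aim 3 asks what marks out high and low sustaining sites. The interviews are sampled on that label, and the quantitative and interview findings are triangulated within the same groups. That is a good reason to keep the label for sampling and triangulation. It does not require the label to be the only regression outcome, and it does not supply the missing cut-off.

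**The analysis is exploratory and secondary.** No power is claimed and no confirmatory decision rests on it. This stands and limits the weight of the point.

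**Scores may bunch at the top.** PRESS is self-reported by staff who delivered SNaP, and Section 8.3 warns that staff may want to show their clinic in a good light. Under a ceiling the gain from the linear model shrinks; under strong left skew it disappears. This also stands, and is why the fix includes a check for skew.

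A reader might be tempted by four stronger conclusions that the documents do not support:
- *That the plan loses a fixed, large amount of power.* The size depends on the association, the split, the test and the score's distribution, none of which is stated.
- *That the logistic analysis inflates false positives.* In these runs the excess is essentially confined to the likelihood-ratio test. Section 8.2.3 names no test, and Wald tests are close to nominal.
- *That the cut-off will be chosen after the scores are seen.* No section says when it will be set. The supportable statement is that it is not pre-specified.
- *That the success label based on fidelity and ART uptake has the same gap.* It has its own stated thresholds.

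**Conclusion.** The point holds in a conditional form. Sustainment is analysed only as a high/low label with no pre-specified cut-off, although each site will have a graded PRESS score.

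Assuming r of 0.3 to 0.5, roughly symmetric site scores, responses from all 42 sites and a median split, the label costs about 12 to 18 points of power for a 5% main-effect test by likelihood-ratio, and more with Wald tests or an uneven split. The cost is about 8 to 9 points with a third of sites at ceiling (individual runs ranged from 6 to 11) and nil under strong left skew. For the planned interaction test it is about 0 to 12 points by likelihood-ratio, nil or reversed under strong skew; the largest loss seen, 14 points, needed slopes of −0.4 and +0.4 in the two arms. The main-effect figures come from a model without the interaction term, because the plan states no main-effect test.

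The missing cut-off is a gap whatever the power figure. Overall this is a cheap improvement to an exploratory secondary analysis; no primary conclusion changes.

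**What to change.** In Section 8.2.3:
- Make the site mean PRESS score the main sustainment outcome, and say how staff answers are combined into it. Fit a linear model with the site characteristic, arm and their interaction, with t-based tests and site as the unit. Section 8.2.1 already uses an identity-link Gaussian model for means such as the fidelity score.
- Add a rank-based or transformed-score check for use if site scores are skewed or at ceiling.
- Keep high/low for selecting the 12 interview clinics and for triangulation.
- If a binary sustainment model is also reported, fix its cut-off, and the handling of middle sites, before PRESS scores are seen.

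The cost is wording only: no new data, participants or procedures. The downside is that results are expressed in PRESS points rather than as odds of being a high sustainer.
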